12.2 Disposition of Patients

Patients who are screened for study entry and do not meet the eligibility criteria will be listed. Reasons for study discontinuation after the start of study treatment will be tabulated.

12.3 Analysis of Primary and Secondary Endpoints

12.3.1 Phase Ib

12.3.1.1 Primary Objective: Safety and tolerability of ACY-1215 monotherapy

Analysis of dose limiting toxicities will be assessed for Arm A and Arm B of the Phase Ib. If more than 1/3 or 2/6 patients experience a DLT, enrollment into the cohort will be stopped. Safety data obtained from this Phase Ib will be analyzed by the sponsor and collaborating investigators to recommend a Phase II dose.

12.3.2 Phase II

12.3.2.1 Primary Objective: Activity Analysis

Efficacy endpoints in this study include defining the proportion of patients with disease response (CR+PR).

CR, PR, and SD are to be determined according to the International Harmonization Project revised Criteria (2007), Patients who discontinue the study before response evaluation will be considered un-evaluable.

In the expansion cohort, analysis for activity in mantle cell lymphoma will be measured for proportion of patients with disease response (CR+PR) determined according to the International Harmonization Project revised Criteria (2007). Patients who discontinue the study before response evaluation will be considered un-evaluable.

For responding patients, the duration of response and time to progression will be reported on a per-patient basis.

Data that may further characterize the activity of ACY-1215 will be summarized and assessed for a potential dose-response relationship.

Overall response rates will be estimated upon completion of the study along with exact 95% confidence intervals.

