Patients will be accrued sequentially to two dose cohorts (Arm A and Arm B) of ACY1215. Upon completion of enrollment of 3 patients to Arm A and a safety assessment has occurred, patients will be allowed to be enrolled to Arm B. All patients will take the assigned dose of ACY1215 for 28 consecutive days. Patients enrolled into Arm A will take ACY1215 160mg once daily, whereas patients enrolled into Arm B will take ACY1215 160mg twice daily. ACY-1215 will be supplied as a liquid for oral administration (PO). Each dose will be administered at least 1 hour after ingestion of food followed by at least 4 ounces of water. Patients will be instructed not to ingest food or other oral medication for at least 2 hours after each ACY-1215 dose.

Phase II:

All patients will take the assigned dose of ACY1215 for 28 consecutive days. The schedule of ACY1215 will be determined based on the safety data from the Phase Ib. Recommended Phase II dose will be based on a discussion with the sponsor and collaborating investigators, with a pre-planned intent to select the schedule that allows the highest dose intensity safely. ACY1215 will be supplied as a liquid for oral administration (PO). Each dose will be administered at least 1 hour after ingestion of food followed by at least 4 ounces of water. Patients will be instructed not to ingest food or other oral medication for at least 2 hours after each ACY-1215 dose.

Duration of Treatment

There is no limit to the number of cycles of therapy. Patients may continue on treatment until they develop progressive disease (PD) or experience an unacceptable toxicity that precludes further treatment.

After discontinuation of therapy, patients will be followed on an every 3 month (+/- 1 week) basis for 1 year or until development of progressive disease or initiation of alternative therapy in order to determine the duration of response.

Patients will be treated until one of the following events:

- Disease progression
- Unacceptable adverse event(s)
- Withdrawal of consent

- General or specific changes in the patient's condition that render the patient unacceptable for further treatment in the judgment of the investigator
- An event that in the judgment of the treating physician warrant's discontinuation of therapy.
- Termination of the study

Study Endpoints

Phase Ib:

The primary endpoint of the study is:

- Establish the safety and tolerability of ACY1215 in two dosing schedules.

Phase II:

The primary endpoint of the study is:

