- The anti-tumor activity of ACY-1215, as measured by:
 - Objective response rate (complete response [CR] + partial response [PR]) assessed according to International Harmonization Project revised Criteria (2007)

Secondary endpoints of the study are to:

- Define the duration of response
- Define the rate of progression free survival
- Define safety and adverse events
- Define the exposure response analyses including biomarkers relating to intracellular protein acetylation.
- Describe the Single- and multiple-dose ACY-1215 pharmacokinetic profile.
- Describe changes in MRS signals with response to study drug

Sample Size

Phase Ib:

Three patients will be sequentially enrolled in one of two cohorts: Arm A and Arm B for a total of six patients (3 in each arm). If $\leq 33\%$ of patients ($N \leq 1$) experiences a dose limiting toxicity (DLT) in a cohort, the cohort will be expanded to 6 patients (3+3). If there are $\leq 33\%$ ($N \leq 2$ DLTs), the cohort will be further expanded to a total of 10 patients (3+3+4). The maximum total number of patients for both Arms A and B with full expansions will total of 20. If more than 1/3 or 2/6 patients experience a DLT, there will be no expansion.

Phase II:

Utilizing the Simon 2 Stage Minimax design, an estimated 40 patients will be needed to determine efficacy at a power of 0.80 and type I error of 0.05. For Stage I, 22 patients

will be enrolled of which 2 must achieve a response to allow for recruitment of patients into Stage 2. Stage 2 will enroll 18 patients of which 8 responses would be needed to attain an efficacy of 25%. An expansion cohort of 20 patients with relapsed or refractory mantle cell lymphoma patients will be assessed to evaluate efficacy in this subtype. The total number of patients accrued to the Phase II component of the study will equal 60.

Safety

Patients will be monitored carefully for the development of adverse events as well as clinical and/or radiographic evidence of disease response. Adverse events will be evaluated according to criteria outlined in the NCI Common Terminology Criteria for Adverse Events (CTCAE), version 4.0.

Figure 1: Schema

[figure not shown]

TABLE OF CONTENTS

	Page
1. OBJECTIVES	1
1.1 Phase Ib	1
1.2 Phase II	1
2. BACKGROUND	1
2.1 Background on lymphoid Malignancies	1
2.2 ACY-1215	2
2.3 Rationale for Phase Ib Study Design	11
3. PATIENT SELECTION	12
3.1 Inclusion Criteria for Lymphoma	12
3.2 Exclusion Criteria	13
3.3 Inclusion of Women and Minorities	13

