1.2.1. Primary Objectives

- Determine the overall response rates (CR plus PR) in patients with relapsed or refractory lymphoid malignancies treated with ACY1215.
- Determine the progression free survival (PFS) and time to treatment failure (TTF) in patients with relapsed or refractory lymphoid malignancies treated with ACY1215.
- Determine the duration of response (DOR) in patients with relapsed or refractory lymphoid malignancies treated with ACY1215.

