12.11 Procedures for Reporting Deviations to Original Statistical Analysis Plan

A formal statistical plan for the analysis and presentation of data from this study will be prepared before database lock. Deviations from the statistical analyses outlined in this protocol will be indicated in this plan; any further modifications will be noted in the final clinical study report.

13. Accrual Rate

We estimate accrual of an average of 6 patients per month across the study centers, with a goal of completing accrual within 12-18 months.

14. Administrative Requirements

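### PFS and TTF are Phase II primary objectives, but as written the analysis section estimates neither: its only time-to-event output is a per-patient report in responders

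*Combined protocol and SAP*

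**What the plan says.** Section 1.2.1 and the synopsis objectives place three items under Phase II primary objectives: overall response rate, PFS with TTF, and DOR. The PFS and TTF item reads "Determine the progression free survival (PFS) and time to treatment failure (TTF) in patients with relapsed or refractory lymphoid malignancies treated with ACY1215", so its population is treated patients, not responders.

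The synopsis heading Study Endpoints is arranged differently. Objective response rate is the only Phase II primary endpoint. DOR is secondary, as is PFS ("Define the rate of progression free survival"). TTF does not appear.

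Section 12.3.2.1 gives the response proportion a full treatment: "Overall response rates will be estimated upon completion of the study along with exact 95% confidence intervals". Its one time-to-event sentence is "For responding patients, the duration of response and time to progression will be reported on a per-patient basis". Section 12.3.2.2, on secondary objectives, covers only pharmacokinetics and pharmacodynamics. Section 12.11 adds: "A formal statistical plan for the analysis and presentation of data from this study will be prepared before database lock".

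**The concern.** The stated method addresses a different quantity from the stated objective. Time to progression in responders leaves out every non-responder. Progression alone also omits deaths, which PFS needs, and treatment stopped for other reasons, which TTF needs. Listing values patient by patient produces no summary estimate.

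Responders are also a selected group, because a patient must remain progression-free until a scan shows response. Patients with stable disease drop out of the report, although section 2.1 presents living with quiescent or stable disease as a result of targeted therapy. Section 2.2.2 says the study should help in powering future combination trials. Progression times from responders alone would be a poor input for that.

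**Working it through.** The plan states no PFS or TTF figure (no median, landmark rate, event count or precision), so there is nothing to reproduce. The check is of the text, followed by a count of who is covered.

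**1. Text side by side**

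| Item | Objectives (1.2.1, synopsis) | Endpoint list (synopsis) | Analysis (12.3.2) |
|---|---|---|---|
| Response rate | Primary | Primary | Proportion, exact 95% CI |
| PFS | Primary | Secondary | None |
| TTF | Primary | Absent | None |
| DOR | Primary | Secondary | Per patient, responders |
| Time to progression | Absent | Absent | Per patient, responders |

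No section gives a start date, event definition, censoring rule, analysis set or estimator for PFS or TTF. Section 12.8 covers only response evaluability, the safety population and the set for drug-specific toxicity.

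**2. Coverage of the responder report**

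Inputs: 40 patients in the two-stage part and 60 with the mantle cell cohort (section 5.1.2, Phase II); unacceptable rate 0.15 and target rate 0.25 (section 12.1.2). Expected responders = N × rate.

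- N = 40: 0.15 × 40 = 6 and 0.25 × 40 = 10, leaving 34 and 30 outside.
- N = 60, if the same rates applied: 9 and 15, leaving 51 and 45 outside.

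So 75% to 85% of patients fall outside the report. Section 12.1.2 also mentions 0.30 in its definition of β; that would give 12 of 40, which does not change the point.

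**3. How different responders could look (assumption only)**

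The documents give no medians. Assume exponential times, non-responder median m₀ and responder median m₁ in months, and response rate p:

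S(t) = p × 0.5^(t/m₁) + (1 − p) × 0.5^(t/m₀).

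The all-patient median solves S(t) = 0.5.

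| p | m₀ | m₁ | All-patient median | 6-month rate, all | 6-month rate, responders |
|---|---|---|---|---|---|
| 0.15 | 2 | 6 | 2.29 | 18% | 50% |
| 0.15 | 2 | 8 | 2.34 | 20% | 59% |
| 0.15 | 3 | 10 | 3.46 | 31% | 66% |
| 0.25 | 2 | 6 | 2.52 | 22% | 50% |
| 0.25 | 2 | 8 | 2.63 | 24% | 59% |
| 0.25 | 3 | 10 | 3.85 | 35% | 66% |

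Example, first row at 6 months: 0.15 × 0.5 + 0.85 × 0.125 = 0.181. The direction follows from assuming that responders progress later. The size follows from the chosen medians.

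**4. What an all-patient estimate would deliver**

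If the 6-month status of all 40 patients were known, the exact 95% interval would be 9.1% to 35.6% for an observed rate of 20%, 16.6% to 46.5% for 30%, and 33.8% to 66.2% for 50%. That is wide but usable for description.

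**The case against.** A reader might infer that the trial cannot estimate PFS or TTF. The documents do not support that. Response scans (sections 5.1.3 and 10.1) apply to all patients. After treatment stops, the synopsis says "patients will be followed on an every 3 month (+/- 1 week) basis for 1 year or until development of progressive disease" or alternative therapy, with no restriction to responders. Reasons for discontinuation are tabulated (section 12.2).

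A reader might also infer that non-responders' times go unreported. Section 12.10 puts all available activity data into listings and tabulations, so what is missing is a summary estimate. Section 12.3.2.1 also promises to summarise other activity data, but too vaguely to supply one.

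Nor is the decision endpoint in doubt. The synopsis names response rate alone as primary, and the sample size and stopping rule rest on it. The mismatch is between the objectives and the endpoints. Section 12.3.2.1 also labels its output as applying to responders, so a misleading figure would need a later mislabelling that the plan does not propose.

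The best defence is the formal plan promised in section 12.11. It leaves room for a cure but does not supply one. Section 12.3.2.2 expressly defers the pharmacodynamic analysis to the statistical analysis plan; nothing comparable is said of PFS or TTF. In an open-label, single-arm trial these definitions are best fixed before outcomes are visible, and database lock comes late for that.

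**Conclusion.** The point stands as a gap in the written analysis that should be corrected. Two quantities listed as primary objectives have no definition, analysis set or estimator, and one of them is missing from the endpoint list. The only time-to-event output covers about 6 to 10 of 40 patients at response rates of 15% to 25%.

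The response-rate decision rule is unaffected. Any numerical contrast between responders and all patients rests on assumed exponential times and medians, and should be quoted only as a range: 2.29 to 3.85 months overall against 6 to 10 months in responders under the settings above. No single figure from that range is supported by the documents.

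**What to change.** In section 12.3.2.1, keep the responder listing and add Kaplan-Meier estimates, with the median and a landmark rate and their 95% confidence intervals:

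- PFS: first dose to progression or death, in all treated Phase II patients.
- TTF: first dose to discontinuation for any reason, progression or death, in the same set.
- DOR: in responders.

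Report the mantle cell expansion cohort separately. State that all treated patients includes those replaced for response assessment under sections 4.5 and 6.1.

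State the censoring rules. They must cover the start of new therapy, where follow-up ends, and the end of the 1-year follow-up. They must also cover patients still event-free at the final analysis, which under section 12.9.2 may come once patients complete 6 cycles.

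Choose the landmark time only after the imaging passages are reconciled. Section 5.1.3 (treatment plan common to both phases) has scans after cycles 2 and 6, then gaps of at most 6 months. Section 10.1 and the study calendar name a scan before cycle 3 and none at cycle 6, with gaps of up to 6 months thereafter. With 28-day cycles, the second scan falls at about week 24 under the first reading and could be as late as about week 34 (8 + 26) under the second. This governs how well progression is dated around 6 months.

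In section 1.2 and the synopsis, name response rate as the only primary endpoint and list PFS, TTF and DOR as secondary.

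The cost is protocol and analysis-plan wording, reconciliation of the scan schedule, and a few tables. No patients are added.

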12.3.2.2 Secondary Objectives

Pharmacokinetic Analysis

Study drug serum concentrations will be determined at all pre- and post-dose timepoints. Parameters to be calculated based on a non-compartmental model approach include:

- C_{\max} .
- Minimum observed serum concentration (C_{\min}).
- T_{\max} .
- Area under the serum concentration time curve (AUC), for time 0 to the last observed value and to the last measurable value, and from time 0 extrapolated to infinity.
- Half-life ($t_{1/2}$).

ACY-1215 serum levels will be tabulated as single- and multiple-PK doses and results will be presented.

Pharmacodynamic Analysis

Details regarding the analysis of pharmacodynamic data will be included in the statistical analysis plan.

12.4 Demographics and Baseline Characteristics

Demographic and baseline disease characteristic data summarization will be performed in order to descriptively assess the outcomes related to lymphoma subtype. Data to be tabulated will include at least demographic features such as sex, age and race, height, and weight as well as disease-specific status and medical history.

12.5 Extent of Exposure

Descriptive statistics for patients treated in and completing each treatment cycle, including the number of doses missed or held and dose reductions required, will be presented for each treatment cycle. Furthermore, descriptive statistics for the number of doses received, percent of expected dose received, and actual dose received will be summarized by treatment cycle. A tabular summary and listing of drug administration and dose intensity by treatment cycle and a by-patient listing of the date and time of each study drug dose and the dose administered also will be presented.

12.6 Concomitant Medications

A tabulation of all concomitant medications will be produced, with concomitant medications coded using the World Health Organization (WHO) drug dictionary. All concomitant medications administered will be presented in a data listing.

12.7 Safety Analysis

Safety evaluations will be based on the incidence, intensity, and type of adverse events, and changes in the patient's physical examination findings, vital signs, ECG findings, and clinical laboratory results. Safety variables will be tabulated and presented for all patients who receive any amount of study drug and have follow-up safety data. Summarization will focus on occurrence rates of: any serious adverse events; treatment-emergent adverse events by system organ class (SOC) and preferred term; discontinuation rates of study therapy due to adverse event or toxicity based on clinical laboratory assessment and rates of hematologic toxicity. The

frequency of DLT by dose cohort also will be summarized.

Adverse events will be coded using the Medical Dictionary for Regulatory Activities (MedDRA) for purposes of summarization. All adverse events occurring on study will be listed in by-patient data listings. Treatment-emergent events will be tabulated, where treatment-emergent is defined as any adverse event that occurs after administration of the first dose of study drug and through 30 days after the last dose of study drug, any event that is considered drug-related regardless of the start date of the event, or any event that is present at Baseline but worsens in intensity or is subsequently considered drug-related by the Investigator.

Events that are considered related to treatment (possibly or probably drug-related) will also be tabulated; it should be noted, however, that without a control the primary safety conclusions must be based on overall incidence rates, not those considered treatment-related.

A tabulation will also be provided that enumerates adverse events by maximum severity.

Deaths, serious adverse events, and events resulting in study discontinuation will be tabulated.

Change from Baseline in clinical laboratory parameters will be summarized across time on study, and the frequency of clinically significant abnormal laboratory values will be tabulated. Shift tables will be produced for selected laboratory parameters, to include at least hemoglobin, WBC count, ANC, absolute lymphocyte count, platelet count, AST, ALT, bilirubin, creatinine, ALP, and electrolytes. These tables will summarize by cycle the number of patients with each baseline CTCAE grade and changes to the maximum CTCAE grade in the cycle.

Changes in vital sign parameters (including systolic and diastolic blood pressure, heart rate, respiration rate, and temperature) will be summarized over time in a similar fashion to laboratory parameters, and any abnormal values will be tabulated. Changes in ECG findings will be presented in data listing format.

Karnofsky/ECOG performance status will be summarized for changes from Baseline to the Final Study Visit; Karnofsky/ECOG performance status on D1 of each treatment cycle will be presented in data listing format.

Additional safety analyses may be determined at any time without prejudice, in order to most clearly enumerate rates of toxicities and to define further the safety profile of ACY-1215.

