2.2.15 Clinical Data

ACY-1215 monotherapy was administered at doses to 360 mg without any observed dose limiting toxicities.. Across all dose levels, the most common treatment-emergent adverse events reported among 15 patients treated with ACY-1215 monotherapy were elevated creatinine (5 patients; 33%), anemia, fatigue, hypercalcemia, and upper respiratory infection (4 patients each;

27%), and cough, diarrhea, dizziness, and low white blood cell count (WBC) (3 patients each; 20%). Of these events, diarrhea and low WBC only occurred at doses ≥ 160 mg. Grade 3 adverse events that were considered by the investigator to be at least possibly related to study drug occurred at doses of 160 mg and 360 mg, and included anemia and decreased WBC and absolute neutrophil count; no Grade 4 events were reported.

Pharmacokinetic analysis of ACY-1215 monotherapy revealed measurable levels of ACY-1215 in all patients, with maximum plasma concentration (C_{max}) levels ranging from 85 ± 39 to 503 ± 195 ng/mL (0.2 to 1.2 μ M) and area under the concentration curve from time 0 to the last time point of quantifiable drug concentration (AUC_{last}) values ranged from 170 ± 61 ng \cdot h/mL to 1093 ± 357 ng \cdot h/mL at dose levels of 40 to 360 mg.[1] Maximal plasma (C_{max}) and exposure (AUC) levels were observed in patients treated at 160 mg (C_{max} 626 ± 150 ng/mL, and AUC_{last} 1074 ± 439 ng \cdot h/mL) and 240 mg (C_{max} 719 ± 329 ng/mL, and AUC_{last} 1231 ± 430 ng \cdot h/mL), suggesting an exposure plateau was reached at dose levels ≥ 160 mg.[1]

The drug was rapidly absorbed (T_{max} ~1 hour) from the gastrointestinal tract. The apparent elimination half-life was ~3 hours. By 24 hours post-dose, drug levels ranged from ~1 ng/mL to below the lower limit of quantification (0.5 ng/mL). There was no accumulation of drug observed over multiple days of administration [28] Overall drug exposure was similar for all doses greater than 160 mg..

Pharmacodynamic analyses in peripheral blood mononuclear cells (PBMCs) revealed acetylation of tubulin at starting at the 40mg dose and that this peaked to a 2-fold increase in acetylated tubulin, the pharmacological marker of HDAC6 inhibition, in all patients at doses of ≥ 160 mg. At doses higher than 160 mg, a modest increase in acetylated histones was demonstrated with ACY-1215 monotherapy.

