7.4.3 AE and SAE Definitions

- **CTCAE term (AE description) and grade:** The descriptions and grading scales found in the revised NCI Common Terminology Criteria for Adverse Events (CTCAE) version 4.0 will be utilized for AE reporting. A copy of the CTCAE version 4.0 can be found online (see http://evs.nci.nih.gov/ftp1/CTCAE/CTCAE_4.03_2010-06-14_QuickReference_8.5x11.pdf).
- **'Expectedness':** AEs can be 'Unexpected' or 'Expected' (see Section 7.2 above) for expedited reporting purposes only.
- **Attribution of the AE:**
 - Definite – The AE is *clearly related* to the study treatment.
 - Probable – The AE is *likely related* to the study treatment.
 - Possible – The AE *may be related* to the study treatment.
 - Unlikely – The AE is *doubtfully related* to the study treatment.
 - Unrelated – The AE is *clearly NOT related* to the study treatment.

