7.4.5 Investigator Reporting to the FDA

The investigator is responsible for reporting any SAEs to the FDA. Serious adverse events (SAEs) that are unlisted/unexpected, and at least possibly associated to the drug, and that have not previously been reported in the Investigators brochure, or reference safety information document should be reported promptly to the Food and Drug Administration (FDA) by [contact]), fax ([name]). Fatal or life threatening SAEs that meet the criteria for reporting to the FDA must be reported to the FDA within 7 calendar days after awareness of the event. All other SAEs that meet the criteria for reporting to the FDA must be reported to the FDA within 15 calendar days after awareness of the event. A clear description of the suspected reaction should be provided along with an assessment as to whether the event is drug or disease related.

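### The treatment-related AE table in section 12.7 names only possible and probable events, so read literally it leaves out those rated Definite

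*Combined protocol and SAP*

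**What the plan says.** Section 12.7 (Safety Analysis) plans a separate table of related events and states in a parenthesis which attributions count: "Events that are considered related to treatment (possibly or probably drug-related) will also be tabulated". The same sentence then limits the table's role. Because the trial has no control group, "the primary safety conclusions must be based on overall incidence rates, not those considered treatment-related".

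Section 7.4.3 (AE and SAE Definitions) gives the attribution scale. Three of its five levels assert a relation to treatment. The strongest reads "Definite – The AE is *clearly related* to the study treatment". Below it stand Probable, for events where a relation is likely, and Possible, for events where one cannot be excluded. The other two, Unlikely and Unrelated, do not assert a relation.

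Two other places set the bar at possible or stronger. Section 7.4.5, on reporting to the FDA, covers unexpected serious events that are "at least possibly associated to the drug". Section 2.2.15, summarising earlier clinical data, describes Grade 3 events "considered by the investigator to be at least possibly related to study drug".

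**The concern.** The parenthesis in section 12.7 reads as a complete list. Nothing marks it as an example or a minimum, and it names two of the three levels that count as related. A programmer who follows it exactly would select Possible and Probable and drop Definite.

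The resulting error can run in one direction only. It lowers the related-event count, and it does so by removing the events with the strongest attribution. An event rated Definite could meet the attribution test for FDA reporting in section 7.4.5 and still be missing from the table of related events. A reader of the study report would assume that a table labelled as treatment-related contains the clearest cases.

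**Working it through.** No stated figure needs to be reproduced. The check is a comparison of text, followed by simple arithmetic on what one omission would do.

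**Step 1. Set the scale against the table rule.**

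| Level in 7.4.3 | Asserts a relation? | Named in the 12.7 parenthesis? | Meets the possible-or-stronger bar of 7.4.5 and 2.2.15? |
|---|---|---|---|
| Definite | Yes | No | Yes |
| Probable | Yes | Yes | Yes |
| Possible | Yes | Yes | Yes |
| Unlikely | No | No | No |
| Unrelated | No | No | No |

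The parenthesis covers 2 of the 3 related levels. No section merges Definite with Probable, and none defines related as Possible or higher for this table.

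**Step 2. Event-level shortfall.** Let R be the number of events rated Possible, Probable or Definite, and D the number of those rated Definite. The table as written shows R − D events, so its proportional shortfall is D/R. The document gives neither D nor R. The shares below are assumptions:

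| Assumed D/R | Shortfall in the table |
|---|---|
| 0% | 0% |
| 5% | 5% |
| 10% | 10% |
| 20% | 20% |

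The shortfall equals the assumed share by construction, so this range is not evidence about the size to expect.

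**Step 3. Patient-level effect.** A patient drops out of the related-event rate only if every related event that patient had was rated Definite. In a row for a single preferred term, the same holds for the patient's related events of that term. The patient-level loss can therefore be smaller than D/R. One such patient changes the rate by 1/n:

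- All planned Phase II patients (22 + 18 + 20 = 60, section 5.1.2): 1/60 = 1.7 percentage points.
- One fully expanded Phase Ib arm (10 patients, section 5.1.1): 1/10 = 10 percentage points.
- Both phases pooled at their planned maxima (20 + 60 = 80): 1/80 = 1.25 percentage points.

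**Step 4. Which other outputs use the parenthesis?** Section 5.1.4 defines dose-limiting toxicity by timing, grade and listed exceptions, without a possible-or-probable filter. The Phase Ib analysis in section 12.3.1.1 uses those toxicities. Section 12.7 also plans treatment-emergent events by system organ class and preferred term, events by maximum severity, tables of serious events, deaths and discontinuations, and by-patient listings of all events. None of these is restricted to Possible and Probable.

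**The case against.** The strongest reply is that the parenthesis is loose drafting. The sentence is about events considered related to treatment, and a Definite event is by definition clearly related. Read alongside sections 2.2.15 and 7.4.5, an incomplete list is more plausible than a deliberate exclusion of the top category. That is probably right about intent, but the instruction as written still produces the wrong table.

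A second reply is that later steps can repair it. Section 12.11 promises a formal statistical plan before database lock, and section 12.7 allows additional safety analyses. Both are true, and both lower the likely harm. That formal plan is not part of the document reviewed, so correction cannot be assumed.

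The third reply concerns consequence, and it stands. Several stronger readings are tempting, and the document does not support them:

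- *That the Phase Ib primary endpoint is biased because safety is that endpoint.* Cohort expansion and the primary analysis rest on dose-limiting toxicities, which this parenthesis does not touch.
- *That the trial as a whole would understate drug toxicity.* Section 12.7 rests its main safety conclusions on overall incidence, and a Definite event still appears in the listings and the unfiltered tables.
- *That one patient is worth 2.5 points, using 40 as the denominator.* Forty is the two-stage response cohort (22 + 18). Section 12.8 defines the safety population as everyone who receives study drug, and the planned Phase II total is 60.
- *That the treatment-emergent table is affected too.* Its definition also admits events considered drug-related whatever their start date, so carrying the parenthesis over could matter for events outside the 30-day window. The document does not link the two, so this is only a further reason to define the term once.

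**Conclusion.** Section 12.7 is wrong as written, with minor severity. The mismatch with section 7.4.3 is certain on the text. Its numerical effect is not known: it is zero if no event is rated Definite, and otherwise a downward shift in one secondary table. The illustrative sizes rest on an assumed Definite share of 0% to 20%, on the planned enrolment, and on the literal reading of the parenthesis. No conclusion about sample size, type I error, power, response rate or dose-limiting toxicity changes.

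**What to change.** In section 12.7, change the parenthesis to *possibly, probably or definitely drug-related*, so that it matches the scale in section 7.4.3. Put the same definition in the formal statistical plan required by section 12.11, and use it wherever an event is called drug-related, including in the treatment-emergent definition.

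The cost is one added term in the protocol text and one consistent definition in the plan. Attribution is already graded on the five-level scale, so no new data are needed. Making the change before database lock also avoids redefining related events after the results of an open-label trial are known.
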